-  Blood samples for determination of hematology and blood chemistry variables and urine dipstick will be collected at Screening Visit, Baseline Visit (before the first study treatment administration), and then every 12 weeks (3 months) from the start of the ITI Period through the time of ITI complete success. If the subject completes the ITI Period in a duration shorter than 12 weeks (3 months), these assessments must be completed at the end of the ITI Period.
-  Dipstick urinalysis, including a protein reading; if the protein reading is positive ( $\geq$ 1+), a full laboratory urinalysis will be required.
-  Sample will be collected and tested if there are no HIV testing results available in the medical history 26 weeks (6.5 months) prior to Screening. HCV and HBV will only be tested at Screening if there is any indication in the medical record that the subject has prior exposure to plasma-derived coagulation factors. For subjects without prior exposure, the sample will be collected and stored at the central laboratory. If the subject is diagnosed with HBV or HCV during the study, this sample will be analyzed by the central laboratory to determine seropositivity at Screening.
-  This assessment is optional, and requires a separate ICF. For subjects whose FVIII mutation and human leukocyte antigen (HLA) allotype is not documented in medical records, samples for analysis of FVIII mutation and HLA allotyping will be collected at the Baseline Visit or at any subsequent visit if blood volume is limited at the Baseline Visit for analysis at the central laboratory.

For Canada specific requirements: see Appendix B.

-  Clinic dosing is applicable only if warranted.
-  Subjects will be advised to delay administration of their daily dose of rFVIIIFc until after the sample for inhibitor testing is taken. For sites that have not yet adopted the Nijmegen-Modified Bethesda Assay, use of the Bethesda Assay is acceptable.
-  A whole blood sample will be collected at Baseline OR Screening, every fourth week during interim ITI Visits, during assessment of ITI outcome visits, and at EOT. A sample for Anti-rFVIIIFc Antibody (ADA) should be collected at Baseline or Screening, and each consecutive visit, except the Week 2 and Safety Follow-Up Visits when allowed by the total volume of plasma that can be collected in one day.

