4 STATISTICAL ANALYSES

4.1 GENERAL CONSIDERATIONS

Continuous data will be summarized using the number of observations available, mean, standard deviation (SD), median, minimum, and maximum. The 25th (Q1) and 75th (Q3) percentiles and 95% confidence intervals may be presented where appropriate. Categorical and ordinal data will be summarized using the count and percentage of patients.

In general, event time variables will be summarized in two ways. For the subset of patients who experience the event of interest, the data will be summarized using standard descriptive statistics for continuous variables as described above. In addition, Kaplan-Meier estimates will be provided for ITI full analysis set regardless whether a patient experiences the event of interest. Patients who do not reach an event will be censored on the date of the last on-study follow-up visit unless otherwise specified in the SAP.

The baseline value is defined as the last available value before the first dose of ITI with rFVIIIFc.

Unless otherwise specified, analyses will be performed for all treated patients.

Observation period

The observation period will be divided into 3 segments:

- **ITI period** starts on the day of the first dose of ITI with rFVIIIFc. For those who successfully tolerized and entered the tapering period, the end of the ITI period is the day before the first visit of the tapering period. For those who did not successfully tolerate per protocol, the end of the ITI period is the day of the last study visit.
- **Tapering period** starts on the day of first visit of the tapering period and ends on the day of the last visit of the tapering period. For those who did not enter the follow-up period, the tapering period ends on the day of the last study visit.
- **Follow-up period** starts on the day after the last visit of the tapering period and ends on the day of the last study visit.

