4.3.4 Supplementary analyses

Additional analyses associated with primary endpoint

Time to negative titer, time to normal incremental recovery, and time to $t_{1/2} \geq 7$ hrs will be summarized using descriptive statistics for patients who meet the criteria for negative inhibitor, normal recovery, and $t_{1/2} \geq 7$ hrs, respectively. Individual patient listing tabulating outcome of ITI treatment, duration on ITI, times to negative inhibitor titer, normal recovery, and tolerization, duration in Tapering Period, duration in Follow-up Period, status of relapse, and duration from ITI success to relapse will be provided.

Factor activity levels from local and central laboratories will be tabulated in individual patient listing by study visit and time points of blood sample. The associated IR in IU/dL per IU/kg, $t_{1/2}$, and the investigator's assessment on whether a patient has met the criteria of IR and $t_{1/2}$ for ITI success will also be tabulated.

Exploratory analysis for the final data

Agreement between local and central laboratory results on the determination on negative titer, normal IR and $t_{1/2} \geq 7$ hrs for ITI success will be summarized. Scatter plots for inhibitor titer will be presented for the ITI period, showing the local laboratory results on the x-axis and the central laboratory results on the y-axis. A line crosses diagonal will be plotted to indicate perfect correlation. Scatter plots for IR in IU/dL per IU/kg and $t_{1/2}$ will be provided by study period.

Time to negative inhibitor

This is defined as the number of days from the first infusion of ITI with rFVIIIFc to the date of first negative titer with a subsequent confirmatory negative titer associated with ITI success.

Time to normal IR

This is defined as the number of days from the first infusion of ITI with rFVIIIFc to the date of first normal IR with a subsequent confirmatory normal IR associated with ITI success.

Time to half life ≥ 7 Hours

This is defined as the number of days from the first infusion of ITI with rFVIIIFc to the date of $t_{1/2} \geq 7$ hours.

Time from negative inhibitor titer to $t_{1/2} \geq 7$ hours

This is defined as the number of days from the date of confirmed negative inhibitor titer to the first date of $t_{1/2} \geq 7$ hours.

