4.4 SECONDARY ENDPOINT(S) ANALYSIS

4.4.1 Key/Confirmatory secondary endpoint(s)

4.4.1.1 Definition of endpoint(s)

ITI Outcome

Each patient will be assigned to one of the following 5 categories of outcomes of ITI treatment.

ITI success

A patient is categorized as an ITI success if the following 3 criteria are all met:

- Confirmed negative titers consisting of 2 consecutive negative inhibitor assessments within 2 weeks (± 3 days) based on local laboratory results <0.6 BU/mL by the Nijmegen-modified Bethesda assay; determination of negative titer based on the Bethesda assay is acceptable at sites that have not yet adopted the Nijmegen-modified Bethesda assay.
- IR ≥ 1.32 IU/dL per IU/kg in 2 consecutive assessments representing $\geq 66\%$ of the expected IR 2 IU/dL per IU/kg.
- $t_{1/2} \geq 7$ hours.

Early withdrawal (outcome not determinable) during ITI period

Unable to determine ITI outcome due to withdrawal prior to completing ITI Period (48 weeks of ITI treatment). For these patients, their status will be further categorized into:

- Positive inhibitor titer
 - Inhibitor titer reduced ($\geq 20\%$) from baseline but not yet negative
 - Inhibitor titer remains the same ($\pm 20\%$) as baseline
 - Inhibitor increased ($\geq 20\%$) from baseline
- Negative inhibitory titer
- Negative inhibitory titer and normal IR

ITI treatment failure (those with at least 36 weeks or 48 weeks of ITI treatment)

Treatment failure is defined for the following two scenarios:

- Patients complete at least 9 months of ITI treatments (Week 36 [Month 9] visit) and experience no downward trend of $\geq 20\%$ in the inhibitor titer comparing to titer at the end of the initial 3 months of treatment (Week 12 [Month 3] visit).
- Patients completed 48 weeks of ITI treatment and inhibitor titer remains positive (≥ 0.6 BU/mL) at Week 48 (Month 12) visit including those who achieve the first negative titer at Week 48 (Month 12) but are not confirmed with a consecutive second negative tier and subsequently with IR ≥ 1.32 IU/dL per IU/kg or $t_{1/2} \geq 7$ hours after 48 weeks of ITI treatment

Patients who have been determined to have failed ITI will then proceed to the End of Treatment (EOT) Visit.

Partial success

The determination of partial success will be made only among patients who have completed the ITI period (Week 48 [12 months] visit) but do not fulfill the criteria for ITI success or treatment failure.

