Partial success is defined as achieving negative inhibitor titer and one of the PK parameters of ITI success: IR ≥ 1.32 IU/dL per IU/kg OR $t_{1/2} \geq 7$ hours.

Patients who have been determined to have achieved only partial success will then proceed to EOT Visit.

Ongoing

This category is only applicable for the interim analysis for the patients who do not meet the definitions for the 4 categories of ITI outcomes as described above. For patients who are ongoing, their status will be further categorized into:

- Positive inhibitor titer
 - Inhibitor titer reduced ($\geq 20\%$) from baseline but not yet negative
 - Inhibitor titer remains the same ($\pm 20\%$) as baseline
 - Inhibitor increased ($\geq 20\%$) from baseline
- Negative inhibitory titer
- Negative inhibitory titer and normal IR

The ITIFAS will be used for this analysis.

Occurrence of relapse after successful ITI

Occurrence of relapse is defined as the proportions of patients who reach ITI success and later meet criteria of relapse during the Tapering Period, Follow-up Period, and the two Periods combined.

Relapse

Relapse is defined as confirmed positive inhibitor titer ≥ 0.6 BU/mL and IR < 1.32 IU/dL after tolerance is achieved, during the Tapering or Follow-Up Periods. The samples for IR derivation need to meet the criteria of 24-hour wash-out period.

Results from local lab will be used for this determination. In the event that the local lab results are not available, the results from the central lab will be used. Occurrence and dates of positive inhibitor titer and loss of normal IR will be recorded in the eCRFs by the investigator.

Time to Relapse

This is defined as the number of days from the date of ITI success to the date of the first confirmed case of relapse.

Number of bleeding episodes

Annualized rate of the number of bleeding episodes during ITI Period will be calculated for each patient in the ITIFAS who had been observed for at least 90 days:

$$\text{annualized bleeding rate} = \frac{\text{number of bleeding episodes}}{(\text{length of study period in days}/365.25)}$$

Bleeding Episode

If a break-through bleed is not resolved right away, a patient may make multiple reports of the same bleed. To determine if multiple reports of bleeds belong to the same bleeding episode, the following definition is to be used.

Bleeds which receive treatment(s)

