4.4.1.2 Main analytical approach

ITI success

The number and proportion of patients achieving complete ITI success, partial success, treatment failure, undetermined, or ongoing with ITI will be summarized.

The ITIFAS will be used for this analysis.

Occurrence of relapse after successful ITI

Occurrence of relapse will be summarized descriptively by calculating the proportions of patients who reach ITI success and later meet criteria of relapse during the Tapering Period, Follow-up Period, and the two Periods combined. The TPFAS will be used for this analysis.

Time to relapse will be defined as the duration between ITI success and time of relapse. Time to relapse from successful ITI will also be summarized descriptively for patients who relapsed during either the Tapering or Follow-Up Period.

Number of bleeding episodes during ITI, Tapering, and Follow-Up Periods

The number of bleeding episodes during ITI Period will be summarized by month using the ITIFAS. Descriptive statistics for annualized bleeding rate while the patients undergo ITI treatment will also be provided. The same analysis will be conducted by whether the bleeding episode is treated, and by type and location of bleeding episodes.

Patients will only be included in this analysis if they were observed for at least 90 days.

The annualized bleeding episodes will also be summarized for the Tapering and Follow-Up Periods using the TPFAS and by patient status of relapse. Detailed results based on whether a bleeding episode is treated, and type and location of bleeding episodes will also be provided.

Number of days away from work or school

If sample size permits ($n \geq 5$), number of days missed from school or work per month will be summarized descriptively for the ITI Period using the ITIFAS and for the combined Tapering and

Follow-Up Periods using the TPFAS. Otherwise, the data will be tabulated in individual patient listing only.

Number of hospitalization days

If sample size permits ($n \geq 5$), number of hospitalization days per year will be summarized descriptively for the ITI Period using the ITIFAS and for the combined Tapering and Follow-Up Periods using the TPFAS. Otherwise, the data will be tabulated in individual patient listing only.

Adherence

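### The 90-day cutoff on the ITI-period annualized bleeding rate, read naturally as ITI time, makes inclusion depend on ITI outcome, and no all-patient rate is planned beside it

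*SAP*

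**What the plan says.** SAP 4.4.1.1 defines the annualized number of bleeding episodes during the ITI Period; it "will be calculated for each patient in the ITIFAS who had been observed for at least 90 days". The formula divides the episode count by the length of the study period in years. SAP 4.4.1.2 first plans monthly counts in the ITIFAS, then the annualized rate during ITI treatment, then breakdowns by treatment, type and location. A separate sentence follows: "Patients will only be included in this analysis if they were observed for at least 90 days".

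SAP 4.1 states that "The observation period will be divided into 3 segments": ITI, Tapering and Follow-up. For tolerized patients, "the end of the ITI period is the day before the first visit of the tapering period". For the others, the ITI period ends at the last study visit.

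Protocol 16.2.2.2 summarizes ITI bleeding by month in the ITIFAS and has no 90-day rule. SAP 4.7.1 applies the same 90-day wording to annualized total consumption, where the denominator is length in study.

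**The concern.** A minimum-observation rule steadies a per-patient annualized rate, because a single bleed over a short period turns into a large number. In this trial, however, the length of the ITI Period is itself a result. A patient leaves it by tolerizing, by being declared a failure at Week 36 or later, by reaching Week 48, or by withdrawing. A cutoff on ITI days can therefore remove the quickest successes and the early withdrawals, but not the failures or partial successes.

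Describing intercurrent bleeding during ITI is a secondary objective, and the protocol plans at most 17 patients. One or two exclusions could move a per-patient mean, and no annualized ITI rate covering everyone treated is planned. Short ITI Periods are foreseen: footnote 4 to protocol Table 1 says what to do about laboratory tests when the period lasts less than 12 weeks.

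**Working it through.** The documents give no derivation for the 90 days, so there is no figure to reproduce. The check is how long an ITI Period can be.

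**Inputs.** After the first negative titer, visits are every 2 weeks (protocol 7.2.2). The first IR sample is drawn at the confirmatory titer visit (Table 1, footnote 13). Two consecutive IR results are needed, then the half-life (7.2.2). The Tapering Initiation Visit is 2 weeks after the half-life visit (7.2.3). The ITI period ends the day before that visit (SAP 4.1).

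**Formula.** With first negative titer at week w, the steps are +2 weeks (confirmation and first IR), +2 (second IR), +2 (half-life) and +2 (first tapering visit). Length = 7 × (w + 8) days, plus 14 for each 2-week retest. The window range uses ±3 days at Week 2, ±7 days at Week 4 or 8, ±3 days at each of the next three visits, and a fixed 14 days to the tapering visit.

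| Path | Nominal ITI days | With windows | One retest (nominal) |
|---|---|---|---|
| First negative Week 2 | 7 × 10 = 70 | 58 to 82 | 84 |
| First negative Week 4 | 7 × 12 = 84 | 68 to 100 | 98 |
| First negative Week 8 | 7 × 16 = 112 | 96 to 128 | 126 |
| Treatment failure, earliest | 36 × 7 = 252 | | |
| Partial success | 48 × 7 = 336 | | |

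Under the ITI-time reading, exclusion among successes needs a first negative titer at Week 2 or Week 4 and almost no repeat testing. Withdrawals before day 90 are excluded on any reading.

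**How many patients?** The documents do not give the share with an ITI Period under 90 days. If it were 5%, 10% or 20% (assumed), the expected number among 17 would be 0.85, 1.7 or 3.4. The chance of at least one, 1 - (1 - q)^17, would be 58%, 83% or 98%. The background figures suggest a low share:
- In the high-dose arm of the randomized study cited in protocol 5.1, the lower quartile was 2.8 months (2.8 × 30.44 = 85 days) to negative titer and 3.5 months (107 days) to normal recovery.
- The three case-report patients in protocol 5.2.3 tolerized at 17 weeks or later. That puts the ITI Period at 17 × 7 + 14 = 133 days or more, so all three would be kept.

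**Size, with assumed bleed rates and 17 patients.** Reported mean against the mean in all 17:
- Fast tolerizers at 2 per year dropped, the rest at 8. One dropped: (2 + 16 × 8)/17 = 7.65, so 8.0 is +4.6%. Two dropped: (4 + 15 × 8)/17 = 7.29, +9.7%.
- Withdrawals at 16 per year dropped, the rest at 6. One dropped: (16 + 16 × 6)/17 = 6.59, so 6.0 is -8.9%. Two dropped: (32 + 15 × 6)/17 = 7.18, -16.4%.
- One of each dropped, the rest at 8: (2 + 16 + 15 × 8)/17 = 8.12, so 8.0 is -1.4%.

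On pooled person-time, with retained patients at 240 days, dropped tolerizers at 77 and dropped withdrawals at 60 (all assumed), two exclusions give:
- Tolerizers: (154 × 2 + 15 × 240 × 8)/(154 + 3,600) = 7.75, so 8.0 is +3.2%.
- Withdrawals: (120 × 16 + 15 × 240 × 6)/(120 + 3,600) = 6.32, so 6.0 is -5.1%.

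**The case against.** **The cutoff is reasonable.** One bleed annualizes to 365.25/28 = 13.0 over 28 days and to 365.25/70 = 5.2 over 70 days. This stands, and the per-patient rate with its cutoff should stay.

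**Much is already reported.** Monthly counts use the ITIFAS, every continuous summary shows its n (SAP 4.1), and SAP 4.3.4 plans an "Individual patient listing tabulating outcome of ITI treatment, duration on ITI, times to negative inhibitor titer, normal recovery, and tolerization". In a study this small, a reader could work out who was left out. That is true, but none of it supplies an annualized rate for everyone treated. The wording of 4.4.1.2 also leaves room to apply the cutoff to the monthly counts.

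**The rule is fully ambiguous.** A reader might infer this, since SAP 4.1 uses observation period for all three segments. The documents lean the other way. SAP 4.4.1.1 puts the cutoff in the same sentence as the ITI Period, and 4.4.1.2 ties the rate to time on ITI treatment. A whole-study clock would also defeat the purpose. A patient with a 70-day ITI Period has about 70 + 336 = 406 days in study, so would be kept and still annualized over 70 days.

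**The rate will be biased upward because fast successes are lost.** A reader might infer this too, but the documents do not support it. The Week 4 exclusion is only nominal, one retest brings such a patient to 98 days, and excluded withdrawals could be poor responders. The median, which SAP 4.1 also requires, does not move in the scenarios above, partly because the retained patients were given identical rates.

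**Ongoing patients are lost as well.** This can happen only at an interim look: "This category is only applicable for the interim analysis".

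**Conclusion.** The point holds as a minor one. On the natural reading, the cutoff makes inclusion in the annualized ITI bleeding rate depend on outcome: the fastest successes and early withdrawals can be dropped, while failures and partial successes nominally cannot. The protocol's own analysis has no such restriction.

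The effect is zero if no ITI Period is shorter than 90 days. Otherwise it is likely to involve a few patients at most, in an unknown direction. The percentages above rest on assumed bleed rates and follow-up times and only show the scale. The endpoint is descriptive, so no error rate or power is affected.

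**What to change.** In SAP 4.4.1.1 and 4.4.1.2:
- Keep the per-patient annualized rate with the 90-day cutoff. State that it means days in the ITI Period and applies to the annualized rate, not to the monthly ITIFAS counts.
- Give the number of patients excluded, by ITI outcome.
- Beside it, report the ITI-period rate for all ITIFAS patients as total episodes divided by total ITI person-time, with a note that this weights patients by ITI duration.

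Do not carry the ITI-days definition into SAP 4.7.1. Consumption there is annualized over length in study, so an ITI-days cutoff would remove fast tolerizers with more than 400 days in study and create the same outcome-dependent exclusion. The cutoff should match the denominator: length in study for the overall rate, and length of the period for any period-specific annualized rate.

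The cost is a few lines of text and one table row. The drawback is two summaries with different weights: two fast tolerizers at 77 days each are 2/17 = 12% of patients but 154/3,754 = 4.1% of person-time in the illustration above.

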4.4.2 Supportive secondary endpoint(s)

Not applicable.

4.5 TERTIARY/EXPLORATORY ENDPOINT(S) ANALYSIS

4.6 MULTIPLICITY ISSUES

Not applicable.

4.7 SAFETY ANALYSES

Safety analyses will either be summarized by study period or listed for all enrolled patients. No statistical testing is planned.

4.7.1 rFVIIIFc exposure

The extent of rFVIIIFc exposure will be assessed by the number of injections, number of days of rFVIIIFc exposure, duration, total amount of consumption, and patient adherence to the regimen, summarized by study period.

Refer to [Section 4.4.1.1](#) for definition of consumption.

Study drug administered

Study drug administered will be listed for all patients. This will include the reason for administration (e.g., regular infusion, IR visit, t_{1/2} visit, other) date and time of administration, dose, and dosing intervals. It will also include lot number and nominal potency of the lots used.

Except for PK doses, the unit body weight dose (IU/kg) for analysis of dosing will be calculated as the total IU (nominal dose) for each injection divided by the patient's most recent weight in kg prior to the dose of study drug.

Dose of 50 IU/kg is to be used for IR and $t_{1/2}$ assessments. The actual dose will be calculated based on the actual potency of the vial (between 80 to 125% of nominal strength) and adjusted by actual volume of infusion if partial vials are used.

$$\text{Dose (IU/Kg)} = \frac{\left(\frac{\text{Total volume administered}}{\text{Volume of vial}} \right) (\text{Actual/Nominal potency of vial})}{\text{Weight(Kg)}}$$

Patients could be infused with the rest of the ITI dose after the 50 IU/kg for IR assessment.

Number of injections and exposure Days

The total number of injections per patient will be summarized descriptively overall and by study period. The number of exposure days is defined as the total number of days in which a patient received infusion during the study and will be summarized descriptively by study period.

Duration of rFVIIIFc exposure

Duration of rFVIIIFc exposure is calculated overall and by study period and is defined as last rFVIIIFc administration date – first rFVIIIFc administration date + 1, regardless of the reason for the last dose or any intermittent interruption. If the date of the last dose of rFVIIIFc is missing, the duration of rFVIIIFc will be left as missing.

Duration of rFVIIIFc dosing (weeks) will be summarized using descriptive statistics overall and by study period.

Prophylactic dose (IU/kg) and dosing interval after ITI success

Patients' first and last doses and dosing frequencies during the tapering period, and the last prophylactic doses and dosing frequencies during the follow-up period will be summarized using TPFAS and FUPFAS, respectively.

Consumption

Total consumption of rFVIIIFc during the study (excluding use of study drug for the purpose of surgery, and for the assessment of IR and $t_{1/2}$) will be summarized descriptively using the ITIFAS. Analysis will also be conducted separately for each of the 3 treatment periods using their respective analysis set. Summary statistics of annualized total consumption will also be provided.

The rate for each patient will be annualized in order to account for difference in the duration of ITI treatment based on the equation below:

$$\text{Annualized total consumption} = \text{total consumption} * \frac{365.25}{\text{length in study (days)}}$$

Patients will be included in this analysis only if they were observed for at least 90 days.

Adherence

Overall adherence to dosing regimen of rFVIIIFc (excluding use for the purpose of surgery and for the assessment of IR and $t_{1/2}$) will be calculated in two ways as follows:

$$\text{Dose adherence (\%)} = \frac{\text{total dose administered as registered in diary and EDC}}{\text{total dose prescribed}}$$

$$\text{Frequency adherence (\%)} = \frac{\text{total number of days with infusions as registered in the diary and EDC}}{\text{total number of days on which infusion was prescribed}}$$

This calculation will be done for each study period, and the results will be listed and summarized descriptively using the respective analysis sets.

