### 6.2. Secondary Objectives and Endpoints

The secondary objectives are as follows:

- To describe the outcome of ITI treatment
- To describe the relapse rate over the 48-week (12-month) period following successful ITI performed with rFVIIIFc
- To describe the intercurrent bleeding during the ITI Period and during the 48-week (12-month) period after successful ITI performed with rFVIIIFc
- To describe the safety and tolerability of rFVIIIFc when used for ITI
- To evaluate the impact of ITI treatment with rFVIIIFc on health economics and adherence

The secondary endpoints are as follows:

- ITI success
  - Confirmed negative titers consisting of 2 consecutive negative inhibitor assessments within 2 weeks ( $\pm 3$  days) based on local laboratory results  $<0.6$  BU/mL by the Nijmegen-modified Bethesda assay; determination of negative titer based on the Bethesda assay is acceptable at sites that have not yet adopted the Nijmegen-modified Bethesda assay
  - IR  $\geq 1.32$  IU/dL per IU/kg in 2 consecutive assessments representing  $\geq 66\%$  of the expected IR 2 IU/dL per IU/kg ([SmPC](#); [USPI](#))
  - $t_{1/2} \geq 7$  hours
- Occurrence of relapse (defined as confirmed positive inhibitor titer  $\geq 0.6$  BU/mL), abnormal recovery after tolerance is achieved, and  $t_{1/2} < 7$  hours) during the Tapering or Follow-Up Periods
- Number of bleeding episodes during the ITI Period and during the 48-week (12-month) period after successful ITI performed with rFVIIIFc
- Adverse events (AEs) and serious adverse events (SAEs)

[figure not shown]
CONFIDENTIAL

The information contained herein may not be used, disclosed, or published without the written consent of  
Bioverativ Therapeutics Inc.

Page 36

- Number of days away from work or school
- Number of hospitalization days
- Adherence (defined as percentage of administered doses versus planned doses)
- Consumption of rFVIIIFc (measured in total rFVIIIFc use)

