### **13.4. Pharmacoeconomic Assessments**

Consumption will be assessed based on the amount of administered study treatment as recorded in the eCRF and in the EPD.

The date and time of the in-clinic administrations of rFVIIIFc will be recorded in the eCRF by the Investigator or designee. The date, time, amount of, and reason for any study treatment administrations done outside the clinic will be recorded by the subject/caregiver in the EPD.

Subject's days missed from school or work will be recorded in the EPD. Hospitalizations will be captured as SAEs.

[figure not shown]

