#### Consumption during ITI

Consumption during the entire study will be summarized descriptively using the ITIFAS. Descriptive statistics will also be provided for each of the periods separately using their respective analysis set.

CONFIDENTIAL

The information contained herein may not be used, disclosed, or published without the written consent of  
Bioverativ Therapeutics Inc.

Page 76

VV-CLIN-0542000 3.0

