Adherence to the treatment regimen at each period is defined in 2 ways. Dose adherence is defined as the percentage of administered doses as registered in the EPD and EDC versus the prescribed doses to a patient. Dosing frequency adherence is defined as the percentage of number of days with infusions as registered in the EPD and EDC compared to the prescribed number of days to a patient in that period.

Consumption during ITI

Consumption of rFVIIIFc at each period is defined as the total rFVIIIFc in IU/kg which is received by a patient in that period.

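### The SAP's consumption analysis leaves out recovery, half-life and surgery doses, although the endpoint is defined as all rFVIIIFc used or received

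*SAP*

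**What the plan says.** Five places define or describe consumption without any exclusion:

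- Protocol 6.2 lists the secondary endpoint as "Consumption of rFVIIIFc (measured in total rFVIIIFc use"). The protocol synopsis and SAP Table 1 use the same wording.
- Protocol 13.4 gives the data source: "Consumption will be assessed based on the amount of administered study treatment as recorded in the eCRF and in the EPD".
- Protocol 16.2.2.2 gives the analysis: "Consumption during the entire study will be summarized descriptively using the ITIFAS", with further summaries by period.
- SAP 4.4.1.1 gives the definition: "Consumption of rFVIIIFc at each period is defined as the total rFVIIIFc in IU/kg which is received by a patient in that period".
- SAP 4.7.1 opens by sending the reader back to 4.4.1.1 "for definition of consumption".

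One place restricts it. SAP 4.4.1.2 contains no consumption analysis of its own and refers to 4.7.1. There, under the Consumption subheading, total consumption is summarized "excluding use of study drug for the purpose of surgery, and for the assessment of IR and" half-life. Annualized consumption is built on the same total. The SAP gives no reason for the exclusion and does not flag it as a departure from the protocol.

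**The concern.** SAP 4.7.1 adopts a definition that counts everything received and then applies a rule that does not, under the same label. A programmer who works from the definition and one who works from the analysis text would report different numbers for the same endpoint.

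The excluded drug is not only test material. Protocol 13.1.2.1 lets the patient have the rest of the daily ITI dose once the recovery sample is taken, so the 50 IU/kg recovery dose is the first part of that day's treatment. If the regimen dose is itself 50 IU/kg, as in the protocol's Table 5 example from week 12, a recovery dose given on a dosing day is the whole of that day's dose, and the exclusion removes it entirely.

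The endpoint serves the health-economics objective, where the amount of product used is itself the result. No planned summary elsewhere gives the all-dose total.

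**Working it through.** The documents state no consumption figure, so there is none to reproduce. The check compares the texts, as set out above, and sizes the gap by arithmetic.

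**Inputs from the documents**
- Assessment dose: SAP 4.7.1 states "Dose of 50 IU/kg is to be used for IR and" half-life.
- ITI dose: 200 IU/kg/day for at most 48 weeks (Protocol 7.2.2). Protocol Table 4 gives 100 IU/kg/day as an example adjusted dose.
- Tapering: Protocol Table 5, an example only, with 100 IU/kg daily, then 100 IU/kg every other day, then 50 IU/kg every other day, changing at weeks 6 and 12 and ending at week 16; thereafter 50 IU/kg three times a week.
- Visits: Protocol Table 2 lists a tapering initiation visit or call and visits at weeks 2, 4, 8, 12 and 16 (5 or 6 recovery doses). Follow-up has recovery at weeks 28 and 40 and a half-life assessment at end of treatment (3 doses).

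**Assumptions**
- First negative titer at week 4, with a recovery or half-life dose at every two-weekly visit after that.
- Fast success: recovery at weeks 6 and 8 and half-life at week 10, so 3 doses.
- Slow course: weeks 6 to 48, so (48 − 6)/2 + 1 = 22 doses.
- Full adherence, and washout and sampling days ignored. Counting two days with only the 50 IU/kg dose in the fast case gives 150/13,650 = 1.10% instead of 1.07%.

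**Formulas**
- Excluded = number of assessment doses × 50 IU/kg.
- Understatement = excluded / total received.

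**Totals received (IU/kg)**
- ITI, fast: 10 × 7 × 200 = 14,000.
- ITI, 48 weeks at 200/day: 48 × 7 × 200 = 67,200.
- ITI, 48 weeks, 100/day from week 4: 4 × 7 × 200 + 44 × 7 × 100 = 36,400.
- Tapering: 6 × 7 × 100 + 6 × 3.5 × 100 + 4 × 3.5 × 50 = 7,000.
- Follow-up: 32 × 3 × 50 = 4,800.

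| Scenario | Received | Excluded | Reported under SAP 4.7.1 | Low by |
|---|---|---|---|---|
| ITI, fast success | 14,000 | 150 | 13,850 | 1.1% |
| ITI, 48 weeks, 200/day | 67,200 | 1,100 | 66,100 | 1.6% |
| ITI, 48 weeks, 100/day from week 4 | 36,400 | 1,100 | 35,300 | 3.0% |
| ITI, never negative | 67,200 | 0 | 67,200 | 0% |
| Tapering, 6 recovery doses | 7,000 | 300 | 6,700 | 4.3% |
| Tapering, 5 recovery doses | 7,000 | 250 | 6,750 | 3.6% |
| Follow-up | 4,800 | 150 | 4,650 | 3.1% |
| Whole study, fast success | 25,800 | 600 | 25,200 | 2.3% |
| Whole study, late success, 100/day | 48,200 | 1,550 | 46,650 | 3.2% |
| Whole study, late success, 200/day | 79,000 | 1,550 | 77,450 | 2.0% |

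The whole-study rows add 7,000 and 4,800 to the ITI total and use 6 tapering and 3 follow-up doses. On a single recovery day the excluded share is 50/200 = 25% or 50/100 = 50% of the daily dose. Annualized consumption is low by the same percentages, because its denominator, length in study, does not change.

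**The case against.** The best defence is that the exclusion is deliberate. SAP 4.7.1 repeats it for adherence, so it is unlikely to be a slip. It is also the only operative analysis text, and a specific rule normally governs a general definition. Regimen consumption is a sensible measure. Half-life testing requires a washout and bars other rFVIIIFc during sampling, and assessment doses are calculated from actual potency while the others use nominal strength. Every administration is listed with its reason, so the full total could be rebuilt. The percentages rest on an example schedule that the protocol leaves to the treating physician. Surgical use should be small, since surgery other than minor procedures leads to withdrawal.

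Much of this is fair. Intent is plausible, the amounts are small, and the surgery share cannot be sized. None of it makes the two texts agree. The SAP does not say that it is reporting regimen consumption, the back-reference in 4.7.1 adopts the definition that counts everything, and a patient listing does not replace the endpoint summary.

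On half-life doses the protocol is not uniform. Section 7.2.2 and Table 2 footnote 12 speak of the remainder of the daily dose afterwards, while 13.1.3.1 speaks of the daily dose. Those passages should be reconciled, but under either wording the drug was received and belongs in a total of drug received.

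**Conclusion.** The concern holds. Followed as written, SAP 4.7.1 produces a figure that is not the endpoint in Protocol 6.2 or the definition in SAP 4.4.1.1.

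The error can only go downward and is uneven: patients who turn negative and have repeated assessments lose most, and those who never turn negative have no scheduled assessment dose and lose nothing. Under the assumptions shown, the whole-study shortfall is about 2.0% to 3.2% for patients who reach ITI success. The largest shortfall for a single period is 4.3%, in tapering. Actual visit counts and individual tapering schedules would move these figures.

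This is a minor point. The endpoint is secondary and descriptive, and no hypothesis test depends on it.

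**What to change.** In SAP 4.7.1, define total consumption as all rFVIIIFc received, in line with 4.4.1.1, and report that as the endpoint, overall, by period and annualized. Add a second row, clearly labelled as consumption excluding recovery, half-life and surgery doses, for readers who want regimen use. A footnote should say that assessment doses are calculated from actual potency and the others from nominal strength.

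The cost is a change of SAP wording and one extra table row. The reason for each administration is already recorded, so no new data are needed. Under the scenarios above, the endpoint figure rises by a few percent at most.
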